6.5 Statistical Methods

This trial was designed with formal statistical hypotheses for both sensitivity and specificity. The sample size was determined based on a fallopian tube-level (each tube will be considered a data point), and assuming a high correlation of 75% between tubes in individual subjects. Previous data suggest that when 1 fallopian tube is positive for malignancy, the subject's other tube is positive about 75% of the time so making a total correlation of 75% is a reasonable assumption.

Since sensitivity is a function of diseased tubes only, while specificity is a function of non-diseased fallopian tubes, the statistical hypotheses for sensitivity and specificity are considered to be independent. Each hypothesis is framed as a 1-sided test with a type I error rate of 2.5%.

For sensitivity, the following hypothesis will be tested:

HNull: Sensitivity \leq 60% versus
HAlternative: Sensitivity $>$ 60%

For specificity, the following hypothesis will be tested:

HNull: Specificity \leq 70% versus
HAlternative: Specificity $>$ 70%

For the sample size calculation, the expected sensitivity of the Cytuity™ device is approximately 80% and the expected specificity is approximately 90%. Based on these parameters and requiring $>$ 80% power for both hypotheses above, 32 subjects positive for malignancy and 18 subjects negative for malignancy are required.¹⁴

Since this is a prospective study in which it is anticipated that the number of subjects testing negative will far exceed subjects testing positive, the sample size calculation is driven by the requirements for the sensitivity hypothesis. Conversion from subjects to fallopian tubes yields a requirement of 56 tubes positive for cancer.¹⁵ Based on an assumed 20% prevalence rate of (subject-level) malignancy, a sample size of 140 subjects (280 tubes) in which both fallopian tubes are tested is statistically likely to produce at least the 56 positive tubes required.

Because the primary analysis is based on fallopian tubes, the analysis must account for the subject-level correlation.¹⁶ A Logistic random-effects model will be used to calculate the point estimates and 95% (2-sided) confidence intervals for sensitivity and specificity.^{17,18} The adjustment proposed by Obuchowski will be performed for comparison.¹³

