6.4 Sample Size Determination

The Cytuity™ procedure will be performed on a maximum of 150 subjects.

Subjects will be recruited until Cytuity™ cytology results can be compared with the surgical histology in at least 32 subjects determined to have a malignant neoplasm or malignancy and 18 subjects determined by surgical histology of the excised tissues to be negative for malignancy.

As this analysis will be conducted on tube level, the sample size was converted to look at the number of tubes that would be required. Previous data suggest that when 1 fallopian tube is positive for malignancy, the subject's other tube is positive about 75% of the time, making a total correlation of 80% is a reasonable assumption. The following formula was used for the statistical conversion:

Statistical conversion from subjects to fallopian tubes yields a requirement of 56 tubes, or samples, positive for malignancy. This is because the left and right fallopian tube are treated as partially independent from one another in regard to the histology results (for example, if there is malignancy in the right tube, that does not mean that there is malignancy on the left).

Based on an assumed 20% prevalence rate of (subject-level) malignancy, a sample size of 140 subjects (280 tubes) in which both fallopian tubes are tested is statistically likely to produce the minimum 56 positive tubes required.

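### The 56-tube requirement is justified by how often both tubes are diseased, whereas the precision of sensitivity depends on the correlation of cytology results between diseased tubes, for which the plan assumes no value

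*Combined protocol and SAP*

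**What the plan says.** Section 6.5 sizes the study for a one-sided 2.5% test of sensitivity (null 60%, expected 80%) and of specificity (null 70%, expected 90%), and states that for more than "80% power for both hypotheses above, 32 subjects positive for malignancy and 18 subjects negative for malignancy are required". It then moves to tubes: "Conversion from subjects to fallopian tubes yields a requirement of 56 tubes positive for cancer". The support is earlier data in which, when one tube is malignant, the subject's "other tube is positive about 75% of the time so making a total correlation of 75% is a reasonable assumption". Section 6.4 draws 80% from the same observation. It explains the conversion by saying that the two tubes are "treated as partially independent from one another in regard to the histology results".

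Section 6.5 says the sensitivity hypothesis drives the sample size. Both sections derive 140 subjects (280 tubes) from the 56 tubes and a 20% subject-level prevalence of malignancy. The recruitment rule in section 6.4 is written in subjects: at least 32 malignant and 18 negative, with at most 150 procedures. The primary analysis is a logistic random-effects model that accounts for within-subject correlation.

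**The concern.** Sensitivity is calculated among diseased tubes only, as section 6.5 itself says. Within that set histology is positive by definition, and what varies is whether cytology detects or misses the malignancy. If a woman has two diseased tubes, the second adds less information the more closely its cytology result follows the first. The correlation of those results, rho, is what inflates the variance. How often disease is present on both sides does not determine rho. It determines only how many diseased tubes each malignant subject contributes.

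The plan gives no value for rho. The preceding study described in section 1.3 cannot supply one, because it reported 100% sensitivity for tubal involvement and so had no misses to correlate. At stake are the justification of the 56 tubes, the 140-subject target derived from them, and the claim of more than 80% power, which depends on an unstated input.

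**Working it through.** **Reproducing the plan's figures**

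- Base number, with the variance taken at the alternative: (1.96 + 0.84)² × 0.8 × 0.2 / 0.2² = 31.4, so 32. The same formula for specificity gives 17.7, so 18.
- Tubes: 32 × (1 + 0.75) = 56 exactly. With the 80% of section 6.4 it would be 57.6, so 58.
- Subjects: 56 / (0.20 × 2) = 140.

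The second step has the form of a design effect for two tubes per subject with correlation 0.75. That is an inference from the exact match, the plan's word correlation and its citation of a clustered-data method, because the formula is not in the available text. The same product is also the expected number of positive tubes from 32 subjects of whom 75% are bilateral. On that reading no allowance for clustering enters at all.

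**What the 75% can supply.** Assume that every malignant subject has at least one positive tube (the documents do not say so), and let q be the share who are bilateral.

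- Per-tube reading (given one diseased tube, its partner is diseased 75% of the time): 2q/(1 + q) = 0.75, so q = 0.6, or 1.6 diseased tubes per malignant subject.
- Per-subject reading (75% of positive subjects are bilateral): q = 0.75, or 1.75 tubes.

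The 75% is not the correlation of disease either. At 20% subject prevalence the phi coefficient is (0.12 − 0.0256)/(0.16 × 0.84) = 0.70 on the per-tube reading, and (0.15 − 0.0306)/(0.175 × 0.825) = 0.83 on the per-subject reading.

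**Design effect with the two inputs separated.** DE = 1 + rho × (Σm²/Σm − 1), where m is the number of diseased tubes in a subject.

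- q = 0.6: Σm²/Σm = 2.8/1.6 = 1.75, so DE = 1 + 0.75 rho.
- q = 0.75: 3.25/1.75 = 1.857, so DE = 1 + 0.857 rho.
- q = 1: 4/2 = 2, so DE = 1 + rho.

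Tubes needed for an effective 32, that is 32 × DE rounded up. The documents give no rho, so the full range is shown.

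| Reading | rho 0 | 0.3 | 0.5 | 0.75 | 1 |
|---|---|---|---|---|---|
| Per-tube 75% (60% bilateral) | 32 | 40 | 44 | 50 | 56 |
| 75% of positive subjects bilateral | 32 | 41 | 46 | 53 | 60 |
| All bilateral | 32 | 42 | 48 | 56 | 64 |

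**Where 56 is enough.** 56/32 = 1.75, so the rho term must not exceed 0.75. This holds up to rho = 1, up to 0.75/0.857 = 0.875, and up to 0.75, for the three rows in turn. Power of 56 tubes by the plan's formula is Φ(0.2 × √(56/DE)/0.4 − 1.96). At rho = 1 it is 81%, 78% and 75% for the three rows. With all bilateral it is 96% at rho = 0, 86% at 0.5 and 81% at 0.75.

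**Subjects.** The 56 tubes need 56/1.6 = 35 or 56/1.75 = 32 malignant subjects. The 140 subjects are expected to give 140 × 0.20 = 28 malignant subjects, hence 28 × 1.6 = 44.8 (about 45) or 28 × 1.75 = 49 positive tubes. The division by 2 in the plan's last step gives 56 only if every malignant subject is bilateral, contrary to either reading of its 75%.

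**The case against.** The strongest reply is that the number is safe even if the reasoning is not. That largely stands. At moderate rho, 56 tubes are more than the formula asks for, and on the per-tube reading they cover every rho from 0 to 1. A reader might infer from the wrong input that 56 is too few. The documents do not support that: power drops below 80% only at high rho combined with a high share of bilateral disease.

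It can also be said that the design-effect mechanism is not on the page. That is right, and it is why the mechanism is stated here as apparent. The alternative reading does not rescue the justification, because it leaves the cytology correlation out altogether.

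Two further limits stand. A reader might infer that the wrong quantity decides when recruitment stops, but the stopping rule is written as 32 malignant and 18 negative subjects; the 56 underlies the 140-subject target. A reader might also infer that the primary analysis is compromised, but the random-effects model takes the within-subject correlation from the trial's own data and does not use the 75%.

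Finally, this may look like the 75% against 80% discrepancy between sections 6.5 and 6.4. It is a separate matter, since reconciling those two values would still leave a figure for disease co-occurrence.

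**Conclusion.** The point holds as a fault in the justification of a sample-size input. The arithmetic reproduces exactly, but the 75% is a probability about histology and is presented as a correlation, while the correlation that governs the precision of sensitivity is never assumed. Depending on that correlation and on the share of bilateral disease, the requirement for an effective 32 lies between 32 and 64 tubes, and 56 is adequate over most of that range. The practical consequence is that the power claim cannot be checked and that the subject figures do not follow from the plan's own co-occurrence figure: 35 or 32 malignant subjects are needed for 56 tubes, against 28 expected from 140.

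This rests on the design-effect reading of 32 × 1.75, on at least one positive tube in every malignant subject, and on taking the plan's base of 32 and its normal-approximation formula as given. Adequate here means adequate by that formula.

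**What to change.** In sections 6.4 and 6.5:

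1. Delete the sentence that equates co-occurrence of disease with correlation, in both the 75% and the 80% form.
2. State whether the 75% is per tube or per positive subject, and use it only for the number of diseased tubes per malignant subject (1.6 or 1.75).
3. State an assumed correlation of cytology results between diseased tubes as an assumption, and apply DE = 1 + rho × (Σm²/Σm − 1).
4. Tabulate the tube requirement, rounded up, for rho from 0 to 1 as above. If 56 is kept, say which rho and which reading it covers. It covers rho = 1 only on the per-tube reading; on the per-subject reading rho = 1 needs 60.
5. Restate the malignant subjects needed for 56 tubes (35 or 32), and the expected yield of 140 subjects at 20% prevalence (28 malignant subjects, about 45 or 49 positive tubes). Carry the same changes into the synopsis.

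The cost is a recalculation and protocol wording, with no new data and no change to the analysis model. The restated subject figures may look less favourable: at 20% prevalence, 32 malignant subjects correspond to 32/0.20 = 160 enrolled and 35 to 35/0.20 = 175, both above the maximum of 150 procedures. A smaller justified rho would lower the tube requirement and so ease this.

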6.1 Hypothesis

As sensitivity is a function of diseased fallopian tubes only, while specificity is a function of non-diseased fallopian tubes, the statistical hypotheses for sensitivity and specificity are considered to be independent. Each hypothesis is framed as a 1-sided test with a type I error rate of 2.5%.

For sensitivity, the following hypothesis will be tested:

H_{Null} : Sensitivity \leq 60% versus

$H_{Alternative}$: Sensitivity $>$ 60%

For specificity, the following hypothesis will be tested:

H_{Null} : Specificity \leq 70% versus

$H_{Alternative}$: Specificity $>$ 70%

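### The claimed power above 80% for sensitivity is about 70% at 32 independent positives once one-sided 2.5% is held, and it is not shown for the 56 tubes

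*Combined protocol and SAP*

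**What the plan says.** Section 6.1 sets the error rate: "Each hypothesis is framed as a 1-sided test with a type I error rate of 2.5" per cent. The sensitivity null is 60% or less, with 80% expected; the specificity null is 70% or less, with 90% expected. Section 6.5 then gives the requirement as more than "80% power for both hypotheses above, 32 subjects positive for malignancy and 18 subjects negative for malignancy are required".

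Section 6.4 moves from subjects to tubes: "Statistical conversion from subjects to fallopian tubes yields a requirement of 56 tubes, or samples, positive for malignancy". The reason given is that "the left and right fallopian tube are treated as partially independent from one another in regard to the histology results". Section 6.5 bases the correlation on disease in the second tube: "other tube is positive about 75% of the time so making a total correlation of 75% is a reasonable assumption". Section 6.4 uses the same 75% observation but arrives at a correlation of 80%.

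On the analysis, section 6.5 says: "A Logistic random-effects model will be used to calculate the point estimates and 95% (2-sided) confidence intervals for sensitivity and specificity". It also says that the sensitivity hypothesis drives the sample size, because "the number of subjects testing negative will far exceed subjects testing positive". No power is stated for 56 correlated tubes under that analysis.

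**The concern.** Sensitivity drives the sample size, so this is the power statement on which the study rests. Two things are doubtful.

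- The 32 appears to come from an approximation that is poor for a proportion near 80% with about 30 observations.
- The step to 56 tubes uses a correlation of the wrong quantity. Sensitivity is estimated only among diseased tubes. Its variance depends on whether cytology agrees between two diseased tubes of one woman, not on how often the second tube is diseased.

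If power is well below 80%, a true sensitivity of 80% would be missed more often than the plan implies, and a non-significant result would be misread. The type I error of the planned test is not in question.

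**Working it through.** **Inputs (sections 6.1, 6.4 and 6.5).** One-sided alpha 0.025; sensitivity 0.60 under the null and 0.80 expected; 32 positive subjects; 56 positive tubes; correlation 0.75 (0.80 in section 6.4); 140 subjects at 20% prevalence.

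**1. Reproducing the plan's 32 and 18.** Using only the alternative variance, n = (z₀.₉₇₅ + z₀.₈₀)² × p₁(1−p₁)/(p₁−p₀)².

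- Sensitivity: (1.95996 + 0.84162)² × 0.16/0.04 = 31.40, so 32.
- Specificity: (1.95996 + 0.84162)² × 0.09/0.04 = 17.66, so 18.
- Nominal power at 32: Φ(0.2 × √32/0.4 − 1.96) = 80.7%.

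The stated figures are therefore no slip of arithmetic.

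**2. Power at 32 with alpha held (exact binomial).**

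| Rule | Type I error at 60% | Power at 80% |
|---|---|---|
| at least 25/32 | 2.48% | 69.8% |
| at least 24/32 | 5.75% | 82.5% |

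This does not depend on choosing an exact test. At 24/32 the score z is 1.73, the logit lower limit is 57.4%, and even the plain Wald lower limit is 59.997%, just short of 60%. All of these need 25/32, so the formula's own Wald test also delivers 69.8%. Exact power first reaches 80% at 45 (34/45, 82.6%). Because counts are discrete it drops to 78.3% at 47; it then stays above 80% from 48 up to 69, the largest number checked.

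**3. The step to 56.** The conversion formula in section 6.4 is missing from the extracted text, so this is inference: 32 × 1.75 = 56, while 0.80 would give 57.6. If 1.75 is a design effect for paired tubes, 56/1.75 = 32 effective observations and the shortfall carries over. If it is the expected number of positive tubes per positive subject, it makes no allowance for correlated cytology results.

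**4. Power with 56 tubes.** The documents do not fix the bilateral/unilateral mix, so three are assumed:

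- 28 pairs: 140 × 20% = 28 subjects.
- 24 pairs + 8 singles: 32 subjects, 24/32 = 75% bilateral.
- 21 pairs + 14 singles: 42 of the 56 positive tubes, or 75%, have a positive partner.

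Let r be the correlation of cytology results within a pair, so that P(both detected) = p² + r·p(1−p), with r the same under null and alternative. Power in %, in the order 28+0 / 24+8 / 21+14:

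| r | Cut-off, r known, size ≤2.5% | Random-intercept logistic, logit-Wald | Random-intercept logistic, likelihood ratio |
|---|---|---|---|
| 0 | 86.4 (all) | 90.4 / 89.5 / 89.5 | 90.4 / 90.6 / 90.2 |
| 0.25 | 83.8 / 84.2 / 84.4 | 82.3 / 83.6 / 83.6 | 82.7 / 84.9 / 85.5 |
| 0.5 | 74.3 / 74.7 / 75.1 | 71.8 / 75.5 / 77.5 | 74.1 / 77.6 / 81.2 |
| 0.75 | 64.4 / 64.7 / 73.9 | 63.5 / 70.0 / 74.4 | 68.9 / 74.8 / 79.2 |

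The cut-off column is exact. The model columns are simulated (6,000 runs per cell) on population-averaged sensitivity, rejecting when the lower limit of the two-sided 95% interval exceeds 60%. Using r = 0.80 lowers the figures by at most 1.8 points compared with 0.75.

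Type I error at r = 0.75:

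- Cut-off: 1.8 / 1.5 / 2.3%.
- Logit-Wald: 1.8 / 1.8 / 2.3%.
- Likelihood ratio: 2.5 / 2.2 / 3.3% simulated. Exact enumeration gives 2.7–2.9%, with power of 69–79%.
- A cluster-adjusted Wald interval (ratio-estimator variance) gives power of 75.2 / 78.0 / 80.0%, but type I error of 3.9%.

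With the cut-off, power falls below 80% once r exceeds 0.26, 0.31 and 0.35 for the three mixes.

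**5. Specificity.** At the minimum of 18 negatives the exact rule is at least 17/18 (size 1.4%), with power 45.0%; 80% is first reached at 31. With the 140 × 80% = 112 negative subjects expected, power is above 99.9%.

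**The case against.** The 32 follows from a standard formula and is only an intermediate step: the primary analysis is at tube level, on 56 positives, with a random-effects model. At tube level the claim may be true. Power is above 80% at a cytology correlation of 0.25, and 81.2% at 0.5 in the most favourable mix with likelihood-ratio limits. It is also awkward to fault the 0.75 as the wrong quantity and then quote power at 0.75. The low end of the range is sensitive to discreteness: for 24+8, a cut-off of 43 instead of 44 gives 73.4% power at size 2.63%, against 64.7% at 1.50%. The likelihood-ratio version of the planned model gives higher figures, up to 79.2%.

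Much of this is fair, and it is why the tube-level claim is called not demonstrated, not false. It does not rescue the statement as written. The plan attaches more than 80% power to 32 and 18 subjects, and at 32 that is not so for any usual test that holds 2.5%. The value 0.75 is the only correlation that section 6.5 offers, so power at that value is the natural conditional figure. The likelihood-ratio range runs slightly above 2.5% and still stays below 80% at 0.75. The specificity minimum is a side issue, since the plan expects many more negatives. The missing conversion formula is not held against the plan.

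**Conclusion.** The concern holds. At 32 independent positives with one-sided 2.5% held, power for sensitivity is 69.8%, not above 80%. For 56 tubes it is about 64–74% if cytology results in paired diseased tubes correlate at 0.75, or 69–79% with likelihood-ratio limits, whose type I error is slightly above nominal. Under the size-controlled cut-off, a true sensitivity of 80% would be missed about 26–36% of the time. Power exceeds 80% only if that correlation is low to moderate: up to roughly 0.26–0.35 with the cut-off, and about 0.5 in the most favourable case.

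The figure at 32 rests only on the plan's own inputs. The tube-level figures rest on two assumptions that the documents do not settle: applying 0.75 to cytology results, and the bilateral/unilateral mix. The test remains valid, so this is a point that should be fixed, not one that undermines the analysis.

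**What to change.** In section 6.5, and wherever section 6.4 and the synopsis rely on it:

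- Replace the sensitivity power claim with about 70% at 32 independent positives, and about 64–74% for 56 tubes if cytology results correlate at 0.75.
- State the formula behind the 32 and 18.
- Say that applying 0.75 to cytology results is an assumption, and reconcile the 75% in section 6.5 with the 80% in section 6.4.
- Add a small table of tube-level power by cytology correlation (0 to 0.8) and bilateral/unilateral mix, preferably simulated under the planned random-effects model with the interval type named.
- For specificity, say that power rests on the roughly 112 negative subjects expected, not on the minimum of 18.

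The cost is a text change and one table. It needs no extra patients and no change to endpoint, alpha or analysis. The drawback is a less favourable stated power for sensitivity.

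### The minimum of 18 negative subjects does not give more than 80% power for specificity at one-sided 2.5%: an exact test at that number has about 45%, though the minimum is unlikely to bind at the assumed prevalence.

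*Combined protocol and SAP*

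**What the plan says.** Section 6.5 frames the specificity test as one-sided at 2.5%, with 70% as the null value and an expected value of about 90%. It asks for more than "80% power for both hypotheses above" and states that "32 subjects positive for malignancy and 18 subjects negative for malignancy are required", citing a textbook but naming no formula. Section 6.4 and the synopsis carry the number into the recruitment rule. Recruitment continues until cytology can be compared with histology in at least 32 subjects with malignancy and "18 subjects determined by surgical histology of the excised tissues to be negative for malignancy", with at most 150 subjects undergoing the procedure.

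Section 6.5 also says that negatives should greatly outnumber positives, that sensitivity drives the sample size, and that 140 subjects at 20% prevalence should supply the 56 positive tubes. The primary analysis is per tube, by a logistic random-effects model with two-sided 95% intervals. The 32 positives are converted to tubes; the 18 negatives are not.

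**The concern.** Specificity is one of the two primary endpoints, and the 18 is the only explicit protection of its sample size. A minimum of this kind matters when the planning assumptions fail. If malignancy is much more common than 20%, the 32 positives arrive early and recruitment may end with few negatives. If 18 does not give the stated power, the rule would then permit a specificity test with a substantial chance of failing even when true specificity is 90%. Readers of section 6.5 would also take from it a power figure that a test holding its error rate does not deliver at that number.

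**Working it through.** **Inputs (section 6.5).** One-sided error 0.025 (z = 1.96); power 0.80 (z = 0.8416); specificity 0.70 under the null and 0.90 expected; between-tube correlation 0.75 (section 6.4 also gives 80%); prevalence 20%.

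**1. Reproducing the plan's number.** The Wald formula with the variance at the alternative only is n = (1.96 + 0.8416)² × p₁(1 − p₁)/(p₁ − p₀)².
- Specificity: 7.849 × 0.09/0.04 = 17.66, rounded up to 18. Nominal power at 18 is 80.7%.
- Sensitivity (0.60 against 0.80): 7.849 × 0.16/0.04 = 31.40, rounded up to 32.

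Both of the plan's numbers reproduce. Using the null variance for the critical value gives ((1.96√0.21 + 0.8416√0.09)/0.2)² = 33.1, or 34. The gap is large because the variance at 70% (0.21) is more than twice that at 90% (0.09).

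**2. What 18 independent negatives deliver.**

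| Rule | Error at 70% | Power at 90% |
|---|---|---|
| ≥17 of 18 (exact or Wilson limit) | 1.4% | 45.0% |
| ≥16 of 18 (Wald limit) | 6.0% | 73.4% |

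The looser rule has more than twice the stated error and still misses 80%. A Wald limit on the logit scale does not help. At 17 of 18 it is 2.833 − 1.96 × √(1/17 + 1) = 0.816, or 69.3%, which is below 70%.

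**3. Tube level.** Eighteen women with two tubes give 36 tubes. The effective number is 36/1.75 = 20.6 at correlation 0.75, or 36/1.80 = 20.0 at 0.80. Beta-binomial simulation at 0.75 gave:
- Wilson limit on the fixed effective number: power 51%, error 1.5%.
- Score limit on an estimated effective number: power 57%, error 2.6%.
- Cluster-adjusted Wald limit: power 79%, error 6.6%.

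These are approximations to the planned analysis. The random-effects model itself was not simulated.

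**4. What number would suffice (exact test, independent negatives).** At n = 31 (reject at ≥27) the error is 2.4% and power 80.7%. Power falls to 73% to 79% for n = 32 to 35. At n = 36 (reject at ≥31) the error is 2.2% and power 85.5%, and power stays at or above 81% for every n from 36 to 49.

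**5. Does the minimum bind?** At 20% prevalence, 140 × 0.80 = 112 negatives are expected, with exact power of 99.97%. The chance of fewer than 36 negatives when the 32nd positive arrives (negative binomial) is about 0.2% at 30% prevalence, 12% at 40% and 69% at 50%. At 64%, the rule is met at about 50 subjects (32/0.64). Prevalences above 20% are illustrations; the documents do not give them.

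**The case against.** **The 18 is not a miscalculation.** A reader might infer an arithmetic slip. The documents do not support that: 18 follows from the plan's inputs by a standard formula, the same one that gives 32. The criticism is of the approximation at this size, and of the text for not naming it.

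**45% is not the trial's power.** A reader might also infer that the trial is underpowered for specificity. It is not, on the plan's assumptions. The minimum is one of two conditions, and the plan expects negatives to far exceed it. Simulating the stopping rule with the 150 cap and a subject-level exact test gives mean specificity power of 99.9% at 20% prevalence, 98% at 30%, 90% at 40% and 82% at 45%. It drops below 80% only between 45% and 50%, more than twice the assumed rate. This part of the objection stands and limits the practical weight of the point.

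**45% is not the planned test.** It takes one observation per subject, while the analysis is per tube. Non-diseased tubes in women with malignancy also count towards specificity. If 56 of the 64 tubes in 32 positive women are diseased, about 8 are not. Counting those as independent gives 20.6 + 8 = 28.6 effective units and exact power of about 67% to 69%. This stands as a reason not to quote 45% alone, but the result is still short of 80%.

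**The missing tube conversion is not itself a shortfall.** The plan's factor gives 18 × 1.75 = 31.5 tubes, and 18 women with two tubes supply 36.

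What remains is that no error-controlling method tried reached 80% at 18. The 20% prevalence is given without a source, while every subject has a mass suspicious for malignancy and section 1.8 calls the population enriched.

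**Conclusion.** The power statement attached to 18 negatives should be corrected. At that number, power is 45% for an exact subject-level test and about 51% to 57% at tube level with limits that hold the error near or below 2.5%. The tube-level range rests on a correlation of 0.75, which the plan derives from malignancy in both tubes and not from agreement of cytology errors in non-diseased tubes, and on approximate intervals in place of the planned model.

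The consequence is small under the plan's own assumptions and becomes real at a prevalence of roughly 40% to 50% or more. The same formula underlies the 32 positives, where exact power is 69.8%. That is a separate point with more bearing on the trial, because sensitivity drives the size.

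**What to change.** In section 6.5, name the formula behind 18 and 32. Then do one of the following, and carry it into section 6.4 and the synopsis:

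- Keep 18 and restate its power as about 45% (exact, subject level), or roughly 50% to 57% at tube level, noting that far more negatives are expected.
- Raise the minimum to a number that gives more than 80% power under an error-controlling test. Thirty-one independent negatives is the first such number (80.7%). Thirty-six is safer, because power dips below 80% from 32 to 35. State any tube conversion as an assumption: at correlation 0.75, 36 × 1.75 = 63 tubes, or 32 women with two tubes; at 0.80, 36 × 1.80 = 64.8, so 65 tubes, or 33 women.

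Either way, a simulation of the planned random-effects model at the chosen minimum would settle the tube-level figure.

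The cost is protocol wording. No extra enrolment is expected at 20% prevalence. With a higher minimum, recruitment could run longer if malignancy is much more common. For example, 36 negatives take on average 36/0.50 = 72 subjects at 50% prevalence and 36/0.36 = 100 at 64%, against 64 and 50 for the 32 positives, all within the 150 cap.
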